**Evobrutinib**

**Phase IIb in Rheumatoid Arthritis  
MS200527-0060**

---

**Evobrutinib**

**Phase IIb in Rheumatoid Arthritis  
MS200527-0060**

---

## Evobrutinib

Phase IIb in Rheumatoid Arthritis  
MS200527-0060

---

### Appendix IV: Protocol Amendment History

The information for the current amendment is on the title page.

The original Protocol version 1.0 was issued on 11 May 2017.

#### Table of Amendments

Amendment Number	Substantial (Y/N)	Date	Region or Country	Included in the current document (Y/N)	Version
Amendment 1	N	03 July 2017	United States	N	1.1
Amendment 2	Y	13 December 2017	Global	Y	2.0
Amendment 3	Y	16 November 2017	United States	N	2.1

## **Evobrutinib**

**Phase IIb in Rheumatoid Arthritis**  
**MS200527-0060**

---

### **Amendment 2**

Protocol Version 1.0 (11 May 2017) was the original global protocol. A global amendment was issued on 13 December 2017.

#### **Rationale and Major Scientific Changes**

Major scientific changes to the protocol were made to add a Japanese cohort, to align the protocol with Japan GCP and local regulatory requirements in Japan, to add fasting requirements, to reduce the Treatment Period from 24 weeks to 12 weeks and remove rescue therapy, to increase safety monitoring by adding visits at Week 6 and Week 10 during the Treatment Period, and to reduce the length of the OLE Period from 24 months to 12 months.

#### **Administrative and Editorial Changes**

Minor editorial changes were made to correct typos, formatting, and stylistic consistency.

## 2 List of Abbreviations and Definition of Terms

Δ	Difference
ACR	American College of Rheumatology
ADaM	Analysis Data Model
AE	adverse event
AESI	adverse event of special interest
ANCOVA	analysis of covariance
ANOVA	analysis of variance
anti-CCP	anti-cyclic citrullinated peptide
ATC	anatomical therapeutic class
BID	twice daily
BMI	body mass index
BOA	biostatistics outputs assembly
BTK	Bruton's tyrosine kinase
CARLOS	cartilage loss scale
CDAI	clinical disease activity index
CFB	change from baseline
CI	confidence interval
CTP	Clinical Trial Protocol
CV	coefficient of variation
DAS28-hsCRP	disease activity score based on 28 joints and high-sensitivity C-reactive protein
CCI	
DMARD	disease-modifying anti-rheumatic drug
DNA	deoxyribonucleic acid
DR	distal radius
DRM	data review meeting
DTS	data transfer specifications
EAIR	exposure adjusted incidence rates
eCRF	Case Report Form, electronic
ECG	electrocardiogram

ESR	erythrocyte sedimentation rate
EULAR	The European League Against Rheumatism
FACIT	functional assessment of chronic illness therapy
HAQ-DI	Health Assessment Questionnaire - Disability Index
HBV	Hepatitis B Virus
HL	Hodges-Lehmann
hrQoL	health-related quality of life
CCI	
hsCRP	high-sensitivity C-reactive protein
IAP	Integrated Analysis Plan
IDMC	Independent Data Monitoring Committee
Ig	immunoglobulin
IMP	investigational medicinal product
ITT	intent-to-treat
IWRS	Interactive Web Response System
JSW	Joint Space Width
LFT	Liver Function Test
LOCF	last observation carried forward
MAR	missing at random
MCID	minimal clinically important difference
MCMC	Markov chain Monte Carlo
MCP	metacarpophalangeal
MCP-MOD	multiple comparison procedures - modeling
MCS	mental component summary
MedDRA	medical dictionary for regulatory activities
mITT	modified intent-to-treat
MMRM	Mixed model with repeated measures
MN	Miettinen-Nurminen
MNAR	missing not at random
MRI	magnetic resonance imaging
MTX	methotrexate
N	number of subjects

---

NCI-CTCAE	National Cancer Institute - Common Terminology Criteria for Adverse Events
NK	natural killer
NSAID	nonsteroidal anti-inflammatory drug
OLE	open-label extension
OMERACT	outcome measures in rheumatology clinical trials
OR	odds ratio
PCR	polymerase chain reaction
PCS	physical component summary
CCI	[REDACTED]
CCI	[REDACTED]
PP	per protocol
[REDACTED]	CCI [REDACTED]
PT	preferred term
Q1	25th percentile
Q3	75th percentile
QD	once daily
QoL	quality of life
RA	rheumatoid arthritis
RAMRIQ	rheumatoid arthritis MRI quantitative
RAMRIS	rheumatoid arthritis magnetic resonance imaging scoring system
RF	rheumatoid factor
ROW	rest of the world
SAE	serious adverse event
SAF	safety analysis set
SCR	screening analysis set
SD	standard deviation
SDAI	simplified disease activity index
SDTM	Study Data Tabulation Model
SF-36	36-item short form health survey
SJC	swollen joint count

SOC	system organ class
TEAE	treatment-emergent adverse event
TJC	tender joint count
TLF	table/listing/figure
ULN	upper limit of normal
VAS	visual analog scale
WHO-DD	World Health Organization drug dictionary

### 3 Modification History

Unique Identifier for IAP Version	Date of IAP Version	Authors	Changes from the Previous Version
Version 1.0	18 April 2019	PPD	NA – first version
Version 2.0	14 October 2019	PPD	
 
• Magnetic Resonance Imaging (MRI) substudy participation removed from the list of covariates in statistical models
 
• Wording for subgroup analyses clarified (See Section 14.3)
 
• Correction of Hochberg procedure terminology in Appendix 18.5
 
• Correction of SAS Sample code for:               
 
• Stratified Miettinen-Nurminen (MN) 95% Confidence Interval (CI),
 
• Mixed model with repeated measures (MMRM),
 
• Logistic regression with repeated measures.
 
 
 
• Correction of Table 43
 
• Correction of Table 53
 
• Addition of MRI Per-Protocol (PP) Analysis Set
 
• Update of PP Analysis Set
 
• Clarification of the wording in Section 15.11
 
• The cumulative proportion of subjects achieving the primary endpoint will be presented as a bar chart instead of a curve (See Section 14.1)
 
• The term “point estimate” has been removed throughout the document and replaced by difference of response rate compared to placebo
 
• The term “Hyperuricemia” has been removed from Table 53, since the parameter will not be analyzed based on Grade values, only normal ranges.
 
• Addition of hsCRP at baseline as a covariate in multiple imputations models as well as joint counts
 
• Addition of a paragraph for actual treatment assignment (See Section 9.1)
 
• Update time window tables for MRI endpoints and ePRO questionnaires
 
• Remove adjusted p-values for supportive analyses (except tipping point analysis)
 
• Add a specific imputation rule for number of missing returned tablets in Section 13
 
• Clarification of the multiple imputation process
 
• Update of total inflammation score for RAMRIQ (See Section 14.2.3).
 
• Addition of imputation rule in case of discrepancies between the two independent readers of MRI scan with regards to RAMRIS data (See Section 14.2.3).
 
• Removal of compliance during the OLE (See Section 13.2)
 

## 4 Purpose of the Integrated Analysis Plan

The purpose of this Integrated Analysis Plan (IAP) is to document technical and detailed specifications for analyses of data collected for protocol MS200527-0060 version 3.0 dated 12 July 2018 and version 2.1 dated 16 November 2017 (US only). The IAP is based upon Section 8 (Statistics) of the trial protocols and is prepared in compliance with International Council for Harmonisation E9.

This version (version 2.0) of the IAP includes details for the final analysis planned at the end of study.

Results of the analyses described in this IAP will be included in the Clinical Study Report (CSR). Additionally, the planned analysis identified in this IAP will be included in regulatory submissions or future manuscripts. Any post-hoc, or unplanned analyses performed to provide results for inclusion in the CSR but not identified in this prospective IAP will be clearly identified in the CSR.

The final clinical database cannot be locked until the final IAP has been approved and signed.

Another document (ms200527-0060-idmc-sap-version1-0-06aug2018) detailed specifications for the Independent Data Monitoring Committee (IDMC) analysis.

## 5 Objectives and Endpoints

Objectives and Endpoints are summarized in [Table 1](#):

[figure not shown]
**Table 1: Objectives and Endpoints**

	Objective	Endpoint	IAP section
Primary Objective	To evaluate the efficacy and dose response of 12 weeks of treatment with evobrutinib compared with placebo in subjects with rheumatoid arthritis (RA) with inadequate response to methotrexate (MTX-IR) on stable MTX therapy by assessment of the signs and symptoms of RA, as measured by American College of Rheumatology (ACR) 20% (ACR20) response assessed using high-sensitivity C-reactive protein (hsCRP) at Week 12.	Primary Endpoint: 
 
ACR20 at Week 12.
 
	Section 14.1
Key Secondary Objectives	To further evaluate the efficacy and dose response of 12 weeks of treatment with evobrutinib in MTX-IR subjects with RA on stable MTX therapy by assessment of the signs and symptoms of RA, as measured by Disease activity score based on 28 joints and high-sensitivity C-reactive protein (DAS28-hsCRP) low disease activity (DAS28 < 3.2) rate at Week 12	Secondary Endpoint: 
 
DAS28-hsCRP < 3.2 at Week 12.
 
	Section 14.2
	To further evaluate the efficacy of 12 weeks of treatment with evobrutinib compared to placebo in MTX-IR subjects with RA on stable MTX therapy by assessment of the signs and symptoms of RA, as measured by DAS28-hsCRP remission (DAS28 < 2.6) rate at Week 12	Secondary Endpoint: 
 
DAS28-hsCRP < 2.6 at Week 12.
 
	Section 14.2
	To further evaluate the efficacy and dose response of 12 weeks of treatment with evobrutinib in MTX-IR subjects with RA on stable MTX therapy by assessment of the signs and symptoms of RA, as measured by ACR50 and ACR70 at Week 12	Secondary Endpoints: 
 
ACR50 at Week 12
 
ACR70 at Week 12.
 
	Section 14.2
	To evaluate the safety of evobrutinib in MTX-IR subjects with RA on stable MTX therapy	Safety Endpoints: 
 
The nature, severity, and occurrence of Adverse Events (AEs) and serious AEs (SAEs)
 
Absolute values and change from Baseline (CFB) in:                             
 
Vital signs
 
Electrocardiogram (ECG) parameters including RR interval,
 
 
 
	Section 15

		
PR interval, QRS duration, QT interval, and QTcF interval
 
 
• Serum Immunoglobulin (Ig) levels (IgG, IgA, IgM)
 
• Total B cell counts
 
• Clinical laboratory parameters.
 
	

Other secondary Objectives
	
To further evaluate the efficacy of evobrutinib on the signs and symptoms of RA with inadequate response to MTX
	
Secondary Endpoints:
 
 
• Clinical Disease Activity Index (CDAI)
 
• Simplified Disease Activity Index (SDAI)
 
• European League Against Rheumatism (EULAR) Responder Index
 
• EULAR Boolean Remission
 
• ACR hybrid score
 
• Changes and percentage changes from Baseline of individual components of the ACR Core Set
 
 
Exploratory Endpoints:
 
CCI [REDACTED]
	
Section 14.2

	
To evaluate the effect of evobrutinib on joint structures and inflammation, at Week 4 and Week 12 in the MRI substudy, as assessed by MRI
	
Secondary Endpoints:
 
 
• Change from Baseline in Outcome Measures in Rheumatology Clinical Trials (OMERACT) Rheumatoid Arthritis Magnetic Resonance Imaging Scoring System (RAMRIS) scores at Week 12 for subjects in the MRI substudy
 
• Synovitis score
 
• Bone marrow edema (osteitis) score
 
 
Exploratory Endpoints:
 
CCI [REDACTED]
	
Section 14.2

		CCI	
	To evaluate the effect of evobrutinib on physical function in RA subjects	Secondary Endpoint: 
 
Health Assessment Questionnaire – Disability Index (HAQ-DI).
 
	Section 14.2
	To evaluate the effect of evobrutinib on subject-reported health-related quality of life (HRQoL)	Secondary Endpoint: 
 
Medical Outcomes Study 36-Item Short Form Health Survey (SF-36).
 
	Section 14.2
	To evaluate the effect of evobrutinib on subject-reported fatigue (using Functional Assessment of Chronic Illness Therapy [FACIT]-Fatigue)	Secondary Endpoint: 
 
FACIT-Fatigue.
 
	Section 14.2
Exploratory Objectives	CCI		

## 6 Overview of Planned Analyses

### 6.1 Independent Data Monitoring Committee review

An IDMC will be set up to continually review available efficacy, safety and tolerability data and will be mandated to make immediate decisions regarding the conduct of the trial; no additional risk minimization measures are proposed. Further details are described in the IDMC charter. Details of the statistical analyses and data presentations for the IDMC meetings are provided in the IDMC Statistical Analysis Plan.

### 6.2 Final Analysis

The final analysis will be triggered when 100% of subjects randomized either complete the Week 12 visit or discontinue prematurely prior to Week 12, the protocol violations are determined, and the database is locked. All data collected from the Safety follow-up visit during the double-blind 12-week treatment period will be included.

Data collected during the OLE period from earlier versions of the protocol will not be part of the Final analysis for the 12 Weeks treatment period but be summarized separately (See Section 7).

## 7 Changes to the Planned Analyses in the Clinical Trial Protocol

- The CTP states a consistency analysis is also planned to be performed as part of the final analysis to evaluate the consistency of efficacy at Week 12 between the Japan and non-Japan subjects.

However, the decision has been taken by the Sponsor not to recruit in Japan. As a result, this consistency analysis will not be performed. Subgroup analysis on Ethnicity Japanese/Non-Japanese will not be performed either.

- In CTP version 2.0, subjects completing the Treatment Period could have entered an optional Open-Label Extension (OLE) period, but the Sponsor made the decision to not initiate the OLE (CTP version 3.0). As a result, some data have been recorded during the OLE for a subset of subjects. Safety and efficacy data from the OLE will then be summarized at the time of final analysis, as detailed in Section 12, 13, 14 and 15.
- The MRI Analysis Set has been redefined to include a pre-dose assessment.

CCI

- The CTP states that the primary endpoint will be evaluated based on a logistic regression model for the odds of ACR20 response, with evobrutinib dose group or placebo as a factor and adjustment for covariates based on randomization strata (region, MRI-substudy participation). This assumed a study design in which subjects could choose whether or not they would participate in the MRI substudy on an individual basis. However, as participation in the MRI substudy was shifted from a per-subject decision to a per-site decision (sites are either MRI or non-MRI), the selection bias is reduced and no clinically significant differences between MRI and non-MRI subjects is expected. Therefore, the adjustment for the covariate of participation in the MRI substudy has been removed. The same change in planned analysis applies for all efficacy endpoints.

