#### Study Population

The proposed trial will evaluate RA subjects with inadequate response to MTX and no prior treatment with biologic DMARD (bDMARD) or targeted synthetic DMARD (tsDMARD [eg, JAK inhibitors, BTK inhibitors]), which we will refer to as the MTX-IR population. Subjects will be randomized to 1 of 3 doses of evobrutinib or placebo.

The MTX-IR population represents a well characterized segment of the total population of individuals with RA, and is one of the populations in which efficacy must be evaluated to obtain approval in the EU per EMA guidance.

Beyond assessing efficacy on clinical endpoints (eg, ACR20 response at 12 weeks, DAS28, ACR core set measures, ACR-EULAR remission), efficacy will also be assessed on physical function (HAQ-DI), pain (VAS), fatigue (FACIT-Fatigue), and HRQoL (SF-36), as these patient-reported concepts are relevant in patients' lives and treatment is expected to impact these variables. Efficacy in preventing structural damage progression will be assessed using MRI in the MRI substudy. Other than the inclusion/exclusion criteria for MRI substudy eligibility, participation in the MRI substudy is purely random, based on MRI availability at a particular site.

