### Stratification Factors at Randomization

Subjects will be stratified by whether or not they are in the MRI substudy and by region to account for the impact on study outcomes of these factors.

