### Use of Magnetic Resonance Imaging to Evaluate Joint Structural Damage Progression

Classically, joint structural damage in RA has been evaluated with radiographic methods, such as the modified Total Sharp Score (mTSS) (van der Heijde 2000). However, these methods are insensitive to early changes, requiring either 1- and 2-year study durations or large studies of shorter duration enriched for patients with documented erosions at Baseline, to assess the ability of an agent to prevent progression of joint structural damage. Due to these limitations, OMERACT developed the RAMRIS, which evaluates wrist and hand MRI images and scores them for erosions, synovitis, tenosynovitis, and osteitis (Ostergaard 2004, Ostergaard 2017). Unlike the mTSS, the OMERACT RAMRIS scores have been shown to be sensitive to changes as early as 12 weeks, and these changes predict radiographic progression as measured by the mTSS (Baker 2014, Baker 2016, Conaghan 2016, Genovese 2016b). Further, these changes have been shown to predict efficacy in longer studies using the mTSS. A validated 9-point scale for the assessment of cartilage loss (CARLOS) (Peterfy 2012) will also be used.

In the proposed trial, approximately 50% of the subjects will be evaluated using MRI to assess treatment effect on the MRI scores at 4 and 12 weeks when compared to Baseline, which we refer to as the MRI substudy. Barring subjects with contraindications to MRI imaging (eg, allergy to MRI contrast, presence of a non-MRI compatible metal medical device or foreign body), participation in the MRI substudy will be required for enrollment at MRI capable sites, in order to avoid selection bias. To ensure an adequate sample size in the MRI substudy, enrollment of non-MRI subjects may be capped. As the non-MRI subjects are projected to be recruited faster than the MRI subjects, capping recruitment of MRI subjects is unlikely to be required. However, if during the course of the study, it appears that MRI subjects will reach 45/arm in advance of the non-MRI subjects reaching 45/arm, we may limit enrollment of further MRI subjects to prevent over enrollment in the MRI substudy.

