## 5.4 Criteria for Randomization and Initiation of Trial Treatment

Randomization should occur on Day 1 after all Screening procedures have been completed; subject eligibility must be reviewed again and confirmed at the site on Day 1 prior to randomization. If a subject does not meet eligibility criteria, the subject can be retested and rescreened once at the Investigator's discretion as described in [Section 7.1.1](#).

Eligible subjects will be randomized to treatment through a central randomization process by an IWRS. This will be a double-blind trial. Subjects will be stratified by whether or not they are in the MRI substudy and by region. There are no systematic differences between MRI and non-MRI sites beyond the availability and suitability of MRI for study purposes, to avoid potential selection bias. Participation in the MRI substudy will be mandatory for subjects participating at designated MRI sites.

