## Evobrutinib

### Phase IIb in Rheumatoid Arthritis MS200527-0060

---

Eligible subjects will be randomized into 1 of 3 evobrutinib arms (25 mg once daily, 75 mg once daily, or 50 mg twice daily) or the placebo arm in a ratio of 1:1:1:1 stratified by whether or not they are in the MRI substudy (Yes, No) and by region (US, Western Europe, Japan, and the rest of world), so that within each treatment arm, there will be approximately 90 subjects, with approximately 45 subjects included in the MRI substudy to ensure approximately 80 evaluable subjects per arm for the primary analysis, and approximately 40 evaluable subjects per arm for the MRI analysis.

To ensure an adequate number of evaluable MRI subjects in the MRI substudy, recruitment of non-MRI subjects into the study may be capped. If a subject's baseline MRI indicates lack of osteitis and synovitis, additional subjects may be added to the MRI stratum to account for these subjects. Should the MRI substudy recruitment prove more difficult than anticipated, the Sponsor reserves the right to terminate the MRI substudy. Should this be done, all sites would be allowed to recruit non-MRI subjects into the study.

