## **8.5.2 Analysis of Primary Endpoint**

### **8.5.2.1 Efficacy Endpoints**

The primary analysis of ACR20 at Week 12 will be based on the mITT analysis set using Last Observation Carried Forward for imputation of missing values of each ACR component. A subject will be considered as a nonresponder if the subject discontinues prior to Week 12.

The estimate of the odds ratio (OR), together with the associated 2-sided 95% CI and p-value, comparing each evobrutinib dose group to placebo, will be provided based on a logistic regression model for the odds of ACR20 response, with evobrutinib dose group or placebo as a factor and adjustment for covariates based on randomization strata (region, MRI-substudy participation). In order to further characterize the dose-response, the proportion of ACR20 response at Week 12 will also be presented for each treatment group, along with the difference in ACR20 response proportion between evobrutinib and placebo, and the 95% CI for the difference. Details will be provided in the SAP.

The dose response will also be assessed via a modeling approach as additional supportive analyses. Details will be provided in the SAP.

Additional sensitivity analyses will be performed to assess the robustness of the primary missing data imputation method and will be described in detail in the SAP.

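### SAP Section 7 drops the MRI randomisation stratum from the primary ACR20 model for a reason that protocol version 3.0 does not support; the effect is small and conservative, and one model term puts it right

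*SAP*

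**What the plan says.** **Randomisation.** Protocol 8.2 has subjects "stratified by whether or not they are in the MRI substudy (Yes, No) and by region". Protocol 5.2.1 gives the purpose: stratifying by MRI-substudy status and "by region to account for the impact on study outcomes of these factors".

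**Protocol model.** Protocol 8.5.2.1 specifies a logistic regression for ACR20 with "adjustment for covariates based on randomization strata (region, MRI-substudy participation" as the closing element. Protocol 8.5.3.1 gives the key secondary endpoints the same approach.

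**SAP model.** SAP 14.1 and the sample code in SAP 18.5 contain treatment and region only. SAP Section 3 dates the change to version 2.0 (14 October 2019). SAP Section 7 explains that the protocol's adjustment presupposed individual choice, that participation later became a per-site matter, that selection bias is therefore lower, and that no clinically significant difference between MRI and non-MRI subjects is expected. It concludes: "Therefore, the adjustment for the covariate of participation in the MRI substudy has been removed". It applies the change to all efficacy endpoints.

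**Participation rule in protocol version 3.0.** Protocol 5.2.1 says "participation in the MRI substudy will be required for enrollment at MRI capable sites, in order to avoid selection bias", with an exception for contraindications. Protocol 5.4 says "Participation in the MRI substudy will be mandatory for subjects participating at designated MRI sites".

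**The concern.** SAP Section 4 states that the plan implements protocol version 3.0 (12 July 2018) and, for the US, version 2.1. The site-level rule that Section 7 cites as the reason for dropping the term is already in version 3.0, next to the instruction to adjust for it. The design fact offered as new was known when the covariate was specified.

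Lower selection bias also answers a different question. The stratum belongs in the model because randomisation was balanced on it. If MRI status predicts response, a model that ignores it overstates the variability of the treatment comparison, so the test becomes conservative and some of the precision bought by stratifying is lost. Some prognostic difference is possible: MRI subjects must also have palpable synovitis in the designated hand (inclusion criterion 16) and must pass a limit on prior surgery or maximum damage in the target hand (exclusion criterion 8b). At stake is a little power in the primary test, and a primary model that departs from the protocol without a sound reason.

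**Working it through.** **1. The plan's own figures.** Inputs from protocol 8.1: 80 evaluable per group, placebo 30% to 45%, benefit 30 or 25 points, chi-squared test, three comparisons. I take α = 0.05/3 = 0.0167 two-sided, so z = 2.394. With p̄ the mean of the two rates,

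power = Φ{ [d√n − z√(2p̄(1−p̄))] / √(p₀(1−p₀) + p₁(1−p₁)) }.

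- 30% vs 60%: (2.683 − 2.394 × 0.7036)/0.6708 = 1.489, so 93.2%.
- 30% vs 55%: (2.236 − 2.394 × 0.6991)/0.6764 = 0.831, so 79.7%.

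Over placebo 30% to 45% this gives 92.9% to 94.0% and 78.6% to 79.7%, against a stated approximate 90% and 80%. A Wald test of the log odds ratio gives 91.0% to 92.0% and 76.9% to 77.8%. Enrolment is 80/(1 − 0.11) = 89.9, so 90. None of these calculations uses a covariate, so the stated power does not depend on the MRI term.

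**2. Power with and without the term.** The documents give no MRI effect, so its odds ratio (OR) is assumed. Two separate simulations of the four-arm logistic model compared region only with region + MRI.

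*Simulation A:* 90 per arm, placebo 37.5%, one dose tested at 0.0167 (the strictest Hochberg step). Assumed: US/Western Europe/rest of world 10/20/70%, half of each region in the MRI stratum, permuted blocks of 8, no region effect; 40,000 trials per scenario.

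| MRI OR | ACR20 gap by MRI status | 25-point benefit: region only → + MRI | 30-point benefit: region only → + MRI |
|---|---|---|---|
| 1.0 | 0 | 83.8% → 83.9% | 95.5% → 95.6% |
| 1.5 | 9.5 points | 83.9% → 84.3% | 95.6% → 95.8% |
| 1.9 | 15 points | 83.9% → 84.8% | 95.7% → 96.0% |
| 2.27 | 19 points | 84.4% → 85.7% | 95.8% → 96.3% |
| 3.0 | 25 points | 84.5% → 86.8% | 96.0% → 96.8% |

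*Simulation B:* 80 per arm, placebo 30%, 25-point benefit for all three doses, the full Hochberg procedure, regions 10/30/60% with mild effects, 4,000 trials. Per-dose power: OR 1.0, 87.1% → 87.2%; OR 1.5, 87.1% → 87.7%; OR 2, 87.0% → 88.8%; OR 3, 88.2% → 90.8%. The largest gain is 90.8 − 88.2 = 2.6 points.

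**3. Type I error.** In simulation B's null runs (placebo 37.5%, 10,000 trials), single-test size for region only is 5.0% at OR 1.0 and 4.2% at OR 3. With the MRI term it is 5.0% to 5.1%. A hand check at OR 3, where the simulated gap is 0.248:

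- Stratum rates are 0.375 ± 0.124, that is 0.251 and 0.499.
- Within-stratum variance is (0.251 × 0.749 + 0.499 × 0.501)/2 = 0.219. Ignoring strata it is 0.375 × 0.625 = 0.234.
- √(0.219/0.234) = 0.967, and 1.96/0.967 = 2.03, a two-sided size of about 4.2% to 4.3%.

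Hochberg family-wise error in simulation A (60,000 null trials per scenario): region only 4.4% to 4.6% at OR 1.0, falling to 3.5% to 3.6% at OR 3.0; region + MRI 4.4% to 4.6% throughout.

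**4. The estimate.** Adding the term makes the odds ratio conditional on MRI stratum as well. In simulation A at MRI OR 2.27 and a 25-point benefit, the mean log OR moves from 1.041 to 1.088 and its standard error from 0.311 to 0.319. The ratio goes from 3.35 to 3.41: the gain comes from the larger conditional effect, not from a smaller standard error.

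**The case against.** The strongest reply is that this hardly matters. At an MRI odds ratio of 1.5 or less the gain is under one point in either simulation; more than two points needs a gap in ACR20 of more than 20 points between MRI and non-MRI subjects. The protocol points away from that: 5.4 says "There are no systematic differences between MRI and non-MRI sites beyond the availability and suitability of MRI for study purposes", and 5.2.1 says that, apart from eligibility, "participation in the MRI substudy is purely random, based on MRI availability at a particular site". Every subject already needs at least six swollen joints, so the extra synovitis criterion may change little. The change is disclosed and dated, protocol 8.5.1 lets the SAP make non-principal changes, and the subgroup models in SAP 14.3 would reveal an MRI effect. All of this stands, and it limits the size of the point. It does not repair the rationale, because version 3.0 makes the same statements and keeps the covariate.

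Three stronger readings are tempting and are not supported.

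- *That the SAP's history is wrong.* Section 7 speaks of an earlier design. US version 2.1 and versions before 3.0 are not available, so it cannot be checked.
- *That the term has gone from every efficacy model and must be restored in all of them.* SAP Table 20 still fits MRI participation and its interaction with treatment. The protocol specifies no ANCOVA, plans only descriptive summaries for SF-36 and FACIT-Fatigue (8.5.3.4), and leaves other efficacy endpoints to the SAP (8.5.3.3). In the RAMRIS models, MRI participation is essentially constant.
- *That the removal inflates type I error.* It does the reverse.

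**Conclusion.** The reason in SAP Section 7 does not support dropping the MRI stratum from the primary model, because the protocol version that the SAP implements already had site-level participation and specified the adjustment. The cost of the omission is about 0 to 2.6 points of power and a single-test size of 4.2% to 5.0%, for an assumed MRI odds ratio of 1 to 3. If MRI status is not prognostic, nothing is lost either way. The ranges also rest on assumed region shares and an even MRI split. The correction is worth making because it returns the primary analysis to the protocol's model at almost no cost, not because the trial's conclusion is in danger. Whether the data have been unblinded cannot be told from the documents.

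**What to change.** Before unblinding:

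1. Add the MRI stratum, with the value under which the subject was randomised in IWRS, as a main effect beside region in the primary ACR20 logistic model (SAP 14.1) and its sample code (SAP 18.5). Report the odds ratio as conditional on both.
2. Reconcile SAP 9.6, which labels the stratum as MRI site but directs the use of participation, with protocol 8.2 and SAP 8.2.3 (Table 3) and 10.1, which name substudy participation.
3. Correct the rationale in SAP Section 7. State there that the stratified Miettinen-Nurminen analyses, including the primary analysis of the key secondary endpoints (SAP Table 15), stay stratified by region only (K = 3), as a declared departure from protocol 8.5.3.1. The reason is sparse strata. With K = 6 and assumed region shares of 5/10/85%, some arm is empty in a stratum in 4.0% (blocks of 4) to 16.2% (blocks of 8) of simulated randomisations, against 0.2% or less with K = 3. With shares of 10/20/70% the K = 6 figure is at most 0.04%, so this is a judgement to be stated openly.

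Adding the term to the ANCOVA (SAP 14.2.2) and the patient-reported outcome models (SAP 14.2.4) is optional alignment. If it is done, the cross-reference that defines the patient-reported MMRM as similar to the RAMRIS model must be edited.

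If the data are already unblinded, keep region only as primary and report region + MRI as a labelled sensitivity analysis.

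The cost is one model term and some SAP wording, with no new data or subjects. The price is an odds ratio conditional on one more covariate.
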